1. Develop an algorithm for using the method of transfusion of hematopoietic umbilical cord blood cells in the treatment of patients with autistic type disorder.
2. To formulate criteria for the selection of patients for this technique.

3. To analyze the efficacy and safety of transfusion of hematopoietic cord blood cells in patients with autistic type disorder using rating scales.
4. Introduce the method of transfusion of cord blood hematopoietic cells to patients with autistic type disorder in the complex therapy of patients with autistic type disorder.

OBJECT OF STUDY

The protocol for testing the method will be carried out on 10 patients with autism spectrum disorder by transfusion of hematopoietic cord blood cells. As a control group, 10 patients with a similar pathology will be examined, comparable in age, gender and degree of autistic disorder according to the “paracopy” type against the background of standard therapy.

Type of study: interventional, prospective, non-randomized with a control group.

Patient selection criteria (indications for this type of treatment):

- age of the patient is from 3 to 15 years.
- Diagnosis: autistic disorder.
- Systemic speech underdevelopment
- The presence of attention deficit hyperactivity disorder as a comorbid state
- Cognitive impairment

Patient exclusion criteria (contraindications for this type of treatment):

- The patient's under 3 years, after 15 years;
- The presence of organic pathology of the brain according to CT, MRI
- The presence of the following diseases in the anamnesis: heart failure in the stage of decompensation, a history of stroke less than 1 year ago, anemia and other blood diseases;
- Decompensation of chronic and endocrinological diseases;
- Acute respiratory viral and bacterial infections, period less than 1 month after the acute phase.
- HIV infection, hepatitis B and C.
- Cancer, chemotherapy and history of cancer;
- Tuberculosis.
- Severe form of intellectual disability as a concomitant disease (diagnosis can be ignored, according to the decision of the Medical Committee of the Center);
- Cerebral palsy.
- Increased convulsive readiness, epilepsy.

Indications and contraindications to this type of treatment for each patient are determined at a consultation of doctors with the participation of a paediatrician or a psychologist (psychiatrist), and transfusiologist.

Research methods

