Evaluation scales CARS, ATEC (to assess the dynamics). Neuropsychological examination, examination of a speech therapist-pathologist. Assessment of neurological status. Determination of the immune status by flow cytometry (CD3; CD4; CD8; CD19; CD16-56). Determination of the level of cytokines in peripheral blood: interleukin 1 beta, interleukin 6, tumor necrosis factor alpha, interleukin 8, gamma interferon. Determination of the HLA genotype of the subject parents and siblings.

The results will be statistically processed using parametric and non-parametric statistics methods using STATA version 9.0, Statistica for Windows version 6.0 and MS Office Excel 2007. Changes from the start of therapy and after 1, 2, 6, 12 months will be compared using the Wilcoxon criterion, comparing data between the main group and the control group using non-parametric method, using the Mann-Whitney test (data are presented in Me - median format with an indication of 25% (q1) and 75% (q3) quartile.

Treatment protocol

Selection of patients and assessment of their psychological status, transfusion of umbilical cord blood HSC in the conditions of day hospital is carried out by specialists of the State budgetary institution of public health "Samara Regional Children's Clinical Hospital N.N. Ivanova Laboratory examination, selection of biomaterial will be carried out by the State Budgetary Institution "MC Dynasty".

Stage 1 - selection and examination of the patient, determination of indications and contraindications to this method of treatment is carried out by a child neurologist, pediatrician (pediatrician), medical psychologist. Assessment of autism disorder is carried out according to the assessment scales of CARS, ATEC.

A prerequisite for inclusion:

- diagnosed with autism spectrum disorder by a psychiatrist,
- Dispensary supervision by a child psychiatrist at the place of residence.

Mandatory general clinical trials (clinical and diagnostic laboratory):

- a) General clinical blood tests (erythrocytes, hemoglobin, platelets, clotting time, leukocytes + formula, COE) - shelf-life 14 days.
- b) general clinical urine test - shelf life 14 days.
- c) feces per helminth eggs - shelf life 14 days.
- d) blood type and rhesus factor.

A patient who meets the selection criteria and has no contraindications for this type of treatment enters into a protocol and signs an informed consent (or his/her legal representative).

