Evaluation of the effect is carried out using the scales used in the introduction to the protocol, evaluation of the neurological and psychological status of the patient.

Evaluation of immune status indicators is carried out 6 months after the last injection.

Cytokine profile is assessed 1, 2, 3 months after the first injection.

Expected results:

It is assumed that transfusions of hematopoietic cord blood cells in patients with autism spectrum disorders will not cause adverse reactions and complications (safe) and will lead to improved social interaction and communication of patients, increased social adaptation, reduced stereotyping, increased self-service skills, increased cognitive functions.

STATISTICAL CONSIDERATIONS

This study will enroll autistic children age 3 to 15 years of age.

Participants will be carried out on 10 patients with autism spectrum disorder by transfusion of hematopoietic cord blood cells. As a control group, 10 patients with a similar pathology will be examined, comparable in age, gender and degree of autistic disorder according to the “paracopy” type against the background of standard therapy.

This is interventional, prospective, non-randomized with a control group study with three intravenous allogeneic, unrelated CB infusion in children ages 3-15 years with ASD/

The primary outcomes will be assessed 1, 2,3,6 and 12 months after the initial infusion in the sequence. Duration of study participation will be 12 months from the time of baseline infusion.

Accrual

It is estimated that up to 2-3 research participants will be enrolled each week and that approximately 4 weeks of accrual will be necessary to enroll 10 participants.

Study Duration

Research participants will be followed for safety for 12 months after the third study infusion.

Demographics and Baseline Characteristics

Demographics and baseline characteristics will be summarized for all research participants. Characteristics to be examined include age, sex, and baseline behavioral status (ATEK).

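### Efficacy rests on behaviour ratings, but no follow-up CARS/ATEC rater is named and no masking is planned, so staff who know the group may score the outcome

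*Combined protocol and SAP*

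**What the plan says.** The Object of study section describes the design as "Type of study: interventional, prospective, non-randomized with a control group". It plans to treat "10 patients with autism spectrum disorder by transfusion of hematopoietic cord blood cells", with 10 comparable children on standard therapy as controls. No sham procedure is described.

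Under Research methods, the outcome tools are listed as "Evaluation scales CARS, ATEC (to assess the dynamics). Neuropsychological examination, examination of a speech therapist-pathologist". Therapy evaluation criteria adds that "Evaluation of the effect is carried out using the scales used in the introduction to the protocol", together with neurological and psychological status. (The introduction reports CARS, CGI and ABC from earlier research, while Research methods names CARS and ATEC; CARS is common to both.)

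On who does what, the Treatment protocol section gives three tasks to one hospital's specialists: "Selection of patients and assessment of their psychological status, transfusion of umbilical cord blood HSC in the conditions of day hospital is carried out". Laboratory work and cord blood sample selection go to a second institution. Stage 1, which covers selection and the decision on indications, "is carried out by a child neurologist, pediatrician (pediatrician), medical psychologist", and the same paragraph prescribes CARS and ATEC. The Object of study section adds a consultation on indications that includes a paediatrician or a psychologist (psychiatrist), and a transfusion specialist.

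Expected results states the assumption that the infusions "will lead to improved social interaction and communication of patients, increased social adaptation".

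No section names who scores CARS or completes ATEC at follow-up, and none mentions masking or an independent rater.

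**The concern.** Behaviour scales depend on judgement, and a rater who knows which children were infused may score them more favourably. Here the direction of any such tilt is clear, because the protocol records benefit as its expectation. The roles most likely to score psychological status also sit in the group that decides who is treated.

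The between-group Mann-Whitney comparison is the only planned analysis that sets treated children against controls. If ratings in one group are tilted, the test cannot separate the tilt from a treatment effect: a 2.8-point tilt and a true 2.8-point benefit look the same in the data. With 10 children per group and no randomisation, nothing else in the design would expose it.

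**Working it through.** The documents give no alpha, power, target effect or SD, so there is no planned figure to reproduce. The check asks how large a tilt would matter.

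**Inputs from the documents**
- 10 treated and 10 control children (Object of study; Statistical considerations).
- Mann-Whitney test between groups (Research methods; Statistical considerations).
- Cited study in the introduction: baseline CARS of about 45 in each group; a fall of 20.0% with cord blood alone and 13.7% in controls.

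**Assumptions**
- Two-sided 0.05 level.
- Normally distributed CARS change with an SD between 3 and 8 points.
- A constant rating tilt in favour of treated children, and no true effect.

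**Step 1: a reference size for the tilt.**
- Cord blood alone: 45 × 0.200 = 9.0 points.
- Control: 45 × 0.137 = 6.2 points.
- Difference: 45 × (0.200 − 0.137) = 45 × 0.063 = 2.8 points.
- Share of the treated fall also seen in controls: 13.7 / 20.0 = 68.5%. The signal is small beside the change common to both groups.

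**Step 2: size of the test.** For 10 v 10 the exact two-sided test rejects when the smaller U is 23 or less. Its exact size is 0.043.

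**Step 3: rejection rate with no true effect.** 20,000 simulated trials per cell:

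| Assumed SD of CARS change | No tilt | 1-point tilt | 2-point tilt | 2.8-point tilt |
|---|---|---|---|---|
| 3 | 4.1% | 9.7% | 26.0% | 46.3% |
| 4 | 4.5% | 7.3% | 16.0% | 29.0% |
| 5 | 4.3% | 6.3% | 11.8% | 19.8% |
| 6 | 4.3% | 5.4% | 9.3% | 15.4% |
| 8 | 4.4% | 4.8% | 7.2% | 10.2% |

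What matters is the ratio of tilt to SD: 0.25 gives about 7%, 0.5 about 16% and 1.0 about 51%.

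**Step 4: effect of masking.** If masked scoring removes the tilt, the rate returns to the no-tilt column, 4.1% to 4.5%. The sample size does not change.

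**The case against.** **The overlap shown is of institution, not of people.** A reader might infer that the same specialists infuse the children and score them. The documents do not say so. The sentence on selection, assessment and transfusion names one hospital and leads into the entry assessment, and the follow-up rater is not stated. This objection stands, and the point is limited to what the plan leaves open.

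**The size of the bias is assumed.** Neither the tilt nor the SD comes from the documents, and at 2.8 points the rate runs from 46% to 10% across the SDs shown. A 1-point tilt does little. The 2.8 points also come from a study with a different route and cell dose. All of this stands. The figures show what is possible, not what will happen.

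**A stated expectation is not evidence of bias.** Expected results is a hypothesis statement. It shows which way a tilt would go, not that one exists.

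**Masking may be harder than it sounds.** The child neurologist, paediatrician and medical psychologist are all Stage 1 selectors, so a reader might wrongly take the medical psychologist to be available as a masked rater under the present roles. Only the speech therapist-pathologist and the neuropsychological examination are listed outside Stage 1, and the documents do not say whether those examiners can rate CARS. Assessments at months 1 and 2 after the first infusion fall about when infusions 2 and 3 are given, with no sham and no time zero described for controls. This raises the cost and makes masking imperfect, but it does not make masked scoring unworkable for 20 children.

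**Other biases remain.** Allocation is not random, families know the treatment, and the within-group Wilcoxon changes have no control. That is true, and it limits what masking can achieve. It is not a reason to leave an avoidable bias in place.

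**Conclusion.** The point holds as a gap in the design. Outcome scoring depends on judgement, it takes place in a plan that puts selection, psychological assessment and infusion in one hospital, and neither the follow-up rater nor any masking is specified.

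If ratings tilted by the whole cord-blood-alone difference in the cited study, a trial with no true effect would reject in about 20% of cases at SD 5 (46% at SD 3, 10% at SD 8), against 4.3%. This rests on an assumed tilt, assumed SDs, normal data and a two-sided 0.05 level.

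A reader might go further and conclude that rater expectation will produce the result. The documents do not support that: they give no evidence of actual bias or its size. The change is worth making because it is cheap and protects the between-group CARS comparison.

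**What to change.** In the Treatment protocol and Therapy evaluation criteria sections, assign follow-up CARS scoring in both groups to one existing examiner who is competent in CARS and takes no part in Stage 1 selection, the treatment consultation or the infusions. Candidates are:
- the speech therapist-pathologist;
- the neuropsychological examiner;
- a psychologist released from Stage 1 and the consultation (the consultation wording already allows a paediatrician or a psychologist).

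Then specify that:
- the rater has no access to infusion records and is not told the group;
- families are asked not to mention treatment;
- scoring takes place away from infusion visits;
- the rater's guess of group is recorded, so that broken masking can be seen;
- the between-group CARS comparison uses these scores;
- the plan states who completes ATEC and, if parents do, that ATEC is unmasked.

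**Cost.** A small change to Stage 1 roles, some scheduling and protocol wording. No extra children and no sham are needed.

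**Limits to state in the plan.** Masking will be weakest at months 1 and 2, and some families may reveal the group. Confounding from non-random allocation, family expectation and the uncontrolled within-group Wilcoxon changes all remain.

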at a dosage of 2 million cells per 1 kg of patient weight (1 intravenous injection, 3 intrathecal with an interval of 5-7 weeks). Group 2 consisting of 9 patients receiving the injections of mononuclear cord blood cells at a dosage of 2 million cells per 1 kg of patient weight and mesenchymal stem cells at a dosage of 1 million cells per 1 kg of patient weight (2 intrathecal and intramuscular injections and 2 intrathecal injections solely). Patients of Groups 1 and 2 received standard rehabilitation therapy. Group 3 consisted of 14 patients receiving standard rehabilitation therapy. The evaluation was conducted 24 weeks after the course of injections. During the treatment, all patients had normal and stable vitals. At the periods of injections or period after them. No allergic or immunological reactions were observed in any patient. There were no deviations from the normal ranges or significant changes in the laboratory indicators of the liver and kidneys functioning, in comparison with the initial level (ALAT, ASAT, bilirubin, urea, and creatinine). Evaluation of the psychological status was made on the CARS scale. The total CARS score was significantly reduced in the Group 2 (a decline of 37.9%); in Group 1, the indicator decreased by 20.0%; in Group 3, i.e. the control group, the indicator decreased by 13.7%. The initial CARS score indicator in each group was at the level of 45. In Groups 1 and 2, there were improvements in behaviour defined for the "Attitude to people", "Body use", "Visual response", "Taste, smell, the reaction on touch and use" and "General Impressions" sub-scales. Those changes were not observed in the control group. The research study proved the safety and effectiveness of the use of cord blood mononuclear cells in the complex treatment of patients. (Transplantation of human cord blood mononuclear cells and umbilical cord-derived mesenchymal stem cells in autism Yong-Tao Lv, Yun Zhang, Min Liu,¹ Jia-na-ti Qiuwaxi,² Paul Ashwood,³ Sungho Charles Cho,⁴ Ying Huan,¹ Ru-Cun Ge,¹ Xing-Wang Chen,¹ Zhao-Jing Wang,² Byung-Jo Kim,⁵ and Xiang Hucorresponding).

\

CLINICAL PURPOSES

Estimation of the safety and efficiency of the method of transfusion of umbilical blood hemopoetic cells to patients with diagnosed autism spectrum disorder without depending on the degrees of compatibility of donor and recipient.

TASKS

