Stage 2 - umbilical cord blood sampling. It is performed by a transfusion doctor of the State Budgetary Institution "MC Dynasty".

The selection criteria for the sample will be the following parameters:

1. Blood group compatibility by system AB0 and Rh
2. Infectious safety (negative HIV test results, hepatitis B and C, syphilis, herpes simplex virus, cytomegalovirus, toxoplasmosis)
3. No bacterial or fungal contamination.
4. Number of hematopoietic cells (mononuclears) in the range of 20-50 million cells per kg of patient weight.

Stage 3 - intravenous injection of hematopoietic cells in umbilical cord blood.

Preliminary examination of the patient and relatives:

- a) Determination of immune status by flow cytometry (SD3; SD4; SD8; SD19; SD16-56) - patient.
- b) Determination of cytokine levels in peripheral blood: interleukin 1 beta, interleukin 6, tumor necrosis factor alpha, interleukin 8, gamma-interferon - patient.
- c) Determination of HLA genotype by loci A, B, DRB1 - patient and parent, sibling.

The sample consists of a suspension of hematopoietic cells diluted in 10 ml 0.9% NaCl + 10 ml 6% hydroxyethyl starch in a disposable syringe labeled by the manufacturer (label).

The patient is injected in drops with the use of infusion. The rate of administration is 60 - 70 ml per hour. Immediately at the beginning of injection, a biological compatibility test should be performed.

Three-fold injection is planned at an interval of 1 month.

Possible area of application

Specialized hospitals.

Data to be obtained during implementation

- correct selection of criteria for selecting patients for treatment of patients with autism type disorder;
- developed algorithm for using the method of transfusion of hematopoietic cells of umbilical cord blood in complex therapy of patients with autism type disorders;
- information on the efficacy and safety of treatment of patients with autism-type disorder by transfusion of hematopoietic cells of umbilical cord blood;
- appropriateness and effectiveness of this method of treatment. To evaluate its impact on treatment tactics and results;
- Association of HLA genes with the development of autism spectrum disorders;
- relationship between immune status and cytokine profile and severity of the disease.

Therapy evaluation criteria

Evaluation of the effect of treatment is carried out 1, 2, 3 and 6 months after treatment.

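### No liver or kidney function blood test is scheduled at any time and no blood count is stated after an infusion, so a safety conclusion could not cover laboratory changes without symptoms

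*Combined protocol and SAP*

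**What the plan says.** **At selection.** Stage 1 asks for "General clinical blood tests (erythrocytes, hemoglobin, platelets, clotting time, leukocytes + formula, COE) - shelf-life 14 days", a routine urine test with the same validity, a stool test, and blood group with rhesus factor.

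**Before and at infusion.** Stage 3 adds lymphocyte subsets, five cytokines and HLA typing, then a compatibility check as the injection starts. On dosing it says: "Three-fold injection is planned at an interval of 1 month". The Stage 2 sample criterion is: "Number of hematopoietic cells (mononuclears) in the range of 20-50 million cells per kg of patient weight".

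**After infusion.** Under Therapy evaluation criteria the only laboratory items are cytokines at 1, 2 and 3 months from the first injection and immune status 6 months after the last. Study Duration adds 12 months of safety follow-up after the third infusion but does not say what it consists of.

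**Safety aims.** Safety appears in the clinical purposes and among the data to be obtained, and Expected results anticipates no adverse reactions or complications. Task 3 reads: "To analyze the efficacy and safety of transfusion of hematopoietic cord blood cells in patients with autistic type disorder using rating scales".

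**Earlier study.** The introduction describes one clinical cell study. Group 1 was treated "at a dosage of 2 million cells per 1 kg of patient weight (1 intravenous injection, 3 intrathecal with an interval of 5-7 weeks". Part of its safety evidence was the absence of significant change in "laboratory indicators of the liver and kidneys functioning, in comparison with the initial level (ALAT, ASAT, bilirubin, urea, and creatinine".

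**The concern.** The plan presents liver and kidney chemistry as safety evidence for the earlier study but schedules none of it for its own children. They are to receive three infusions of unrelated donor cells, at a higher dose and by another route.

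Followed exactly, the plan could report the reactions that staff or families notice. It could not show whether liver enzymes, creatinine or haemoglobin had shifted without symptoms. A conclusion that the method is safe would be silent on these effects and could not be set beside the laboratory result in the introduction. For the individual child, a silent change after infusion 1 or 2 might go unseen before the next infusion.

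**Working it through.** The plan gives no figure to reproduce here. The check is a reading of the schedule, a dose comparison, and the size and limits of the remedy.

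**1. Tests against the schedule**

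| Test | Selection | Before infusions 2 and 3 | After infusion 3 |
|---|---|---|---|
| ALAT, ASAT, bilirubin, urea, creatinine | no | no | no |
| Blood count | yes | not stated | no |
| Routine urine test | yes | not stated | no |
| Cytokines | yes (Stage 3) | yes (months 1, 2) | yes (month 3) |
| Immune status | yes (Stage 3) | no | yes (6 months after last injection) |

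Liver and kidney blood tests scheduled: 0 of 5.

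**2. Infusions followed by a blood count**

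Infusions: 10 children × 3 = 30.
- If the 14-day limit applies at entry only: 0 of 30.
- If it forces a repeat before infusions 2 and 3: 10 × 2 = 20 of 30.
- After the third infusion: 0 of 10 on both readings.
- With counts at months 1, 2 and 3: 30 of 30. Infusions fall at about months 0, 1 and 2, so each draw comes about one month after an infusion.

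**3. Dose (million cells per kg, course totals)**

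Neither the plan nor its account of the earlier study says whether the dose is per injection or per course, so every pairing is shown for Group 1 (four injections).

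| This trial | Earlier study | Ratio |
|---|---|---|
| per infusion: 3 × 20 to 3 × 50 = 60 to 150 | per injection: 4 × 2 = 8 | 7.5 to 18.75 |
| per infusion: 60 to 150 | whole course: 2 | 30 to 75 |
| whole course: 20 to 50 | per injection: 8 | 2.5 to 6.25 |
| whole course: 20 to 50 | whole course: 2 | 10 to 25 |

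Per single administration, the lowest Group 1 ratio is (20/3)/2 = 3.3.

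Group 2 also received mesenchymal cells (1 million per kg). Counting both types (3 million per kg), the lowest course ratio is 20/(4 × 3) = 1.67. If each dual-route session counts as two administrations, giving six, it is 20/(6 × 3) = 1.11. No reading falls below 1.

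**4. What 10 treated children can show once tested**

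Probability of seeing at least one event is 1 − (1 − p)^10. For assumed true rates p of 5%, 10% and 20% it is 40%, 65% and 89%. With 0 of 10, the one-sided 95% upper bound is 1 − 0.05^(1/10) = 0.259, about 26%.

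**5. Chance flags before infusions 2 and 3**

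Checks: 10 × 2 = 20. Assume independent values, each out of range by chance with probability 2% to 5%.
- 11 values (5 chemistry + 6 count items): 1 − 0.98^11 = 0.199 and 1 − 0.95^11 = 0.431, so 4.0 to 8.6 of 20.
- 16 values (leukocyte formula counted as five fractions): 1 − 0.98^16 = 0.276 and 1 − 0.95^16 = 0.560, so 5.5 to 11.2 of 20.

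Overall, about 4 to 11 of the 20 checks.

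**The case against.** Several stronger readings are tempting, and the documents do not support them.

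- **That kidney function is never looked at.** The urine test at selection is a crude kidney screen. It does not replace urea or creatinine, and no repeat is stated.
- **That safety is not assessed, or rests on rating scales alone.** Task 3 names only rating scales, possibly through loose translation, but adverse reactions and a 12-month safety follow-up appear elsewhere. Clinically apparent harm could be recorded. What stays uncovered is laboratory change without symptoms.
- **That no blood count can follow any infusion.** A 14-day result has lapsed by the time a monthly infusion is due, so renewal before infusions 2 and 3 is plausible, though not stated. The gap after infusion 3 remains.
- **That the plan contradicts its own anaemia contraindication.** The exclusion covers a history of "heart failure in the stage of decompensation, a history of stroke less than 1 year ago, anemia and other blood diseases", judged at selection. Nothing makes it a rule for re-dosing.
- **That a pre-infusion review already exists.** The plan says: "Indications and contraindications to this type of treatment for each patient are determined at a consultation of doctors with the participation of a paediatrician". The sentence goes on to allow a psychologist or psychiatrist in the paediatrician's place, adds a transfusiologist, and concerns eligibility. A review before re-dosing would be a new step.
- **That the higher dose signals organ harm.** The documents give no such signal, and the one laboratory result described was null. The ratio runs from 1.1 to 75 and the routes differ, so no single multiple should be quoted. The comparison shows only that the earlier result cannot stand in for testing here.

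It is also fair to say that 10 children and monthly samples yield limited information, and that the introduction does not say when the earlier study took its samples, so comparability in time stays uncertain. This limits what the remedy can claim. It does not justify leaving the tests out of a trial with safety as a stated purpose.

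**Conclusion.** The point holds for laboratory changes without symptoms. In the visible text, 0 of the 5 liver and kidney blood tests used as earlier safety evidence are scheduled. Between 0 and 20 of 30 infusions are followed by a blood count, depending on how the 14-day limit is read, and none of the 10 third infusions is.

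A conclusion of safety drawn from this plan could cover recorded reactions. It could not cover silent liver, kidney or blood-count effects, nor be compared with the earlier laboratory finding. That finding does not carry over: the planned dose is higher on every like-for-like reading, and Group 1 had three of its four injections intrathecally whereas this trial is all intravenous.

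This is worth correcting before treatment starts, because the remedy is cheap and bears on the children's safety as well as on the report. The conclusion assumes that no further tests are set out in parts of the protocol that are not public.

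**What to change.** For treated children:

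1. Add ALAT, ASAT, bilirubin, urea and creatinine at baseline and at 1, 2 and 3 months, and the Stage 1 blood count at 1, 2 and 3 months, on the cytokine draws already planned.
2. Take the 1- and 2-month samples before infusions 2 and 3. Add a short review by the paediatrician and transfusiologist, postpone an infusion only for a change they judge clinically significant, and record the decision.
3. At each time, report the number of children outside the normal range and the change from baseline (median and quartiles).
4. Reword Task 3 so that rating scales serve efficacy, while recorded adverse reactions and these tests serve safety.
5. State whether the 14-day limit requires a repeat before each infusion, and whether the cell dose is per infusion or per course.

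**Cost.** Chemistry panels: 10 × 4 = 40. Added counts: 10 × 3 = 30, or 30 − 20 = 10 if repeats are already required. Up to 20 visits would move slightly earlier if results are not ready the same day. About 4 to 11 of the 20 pre-infusion checks would show a chance out-of-range value needing review, and an occasional postponement would stretch the monthly interval. Sample size, dose and length of follow-up do not change.

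**Limits that remain.** Changes that resolve within a month would be missed. No control samples are requested, so abnormalities would be described, not attributed to treatment. The 26% upper bound should be reported alongside any finding of 0 in 10.

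### The planned cell dose exceeds the only human cord blood dose the plan describes, and no safety check or stopping rule governs the next infusion or the next child

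*Combined protocol and SAP*

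**What the plan says.** **Dose.** The fourth sample criterion in Stage 2 is "Number of hematopoietic cells (mononuclears) in the range of 20-50 million cells per kg of patient weight". Stage 3 describes the sample as a suspension in one syringe and sets the schedule: "Three-fold injection is planned at an interval of 1 month". The text does not say whether the range is per infusion or per course. Statistical Considerations specifies "three intravenous allogeneic, unrelated CB infusion". Clinical Purposes states the aim of assessing the method "without depending on the degrees of compatibility of donor and recipient".

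**Human precedent.** The background describes one clinical study of these cells. Its Group 1 (14 patients) was treated "at a dosage of 2 million cells per 1 kg of patient weight (1 intravenous injection, 3 intrathecal with an interval of 5-7 weeks". The 9 patients in Group 2 had the same mononuclear dose plus mesenchymal cells. No allergic or immunological reactions were reported.

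**Safeguards before or at infusion.** A consultation that includes a transfusion specialist settles each patient's indications and contraindications. Stage 2 requires AB0 and Rh compatibility, negative infection tests and no bacterial or fungal contamination. Stage 3 adds a compatibility test as the injection begins.

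**Follow-up.** Therapy Evaluation Criteria says "Evaluation of the effect of treatment is carried out 1, 2, 3 and 6 months after treatment". Statistical Considerations instead times the primary outcomes from the first infusion. Cytokines are measured 1, 2 and 3 months after the first injection, and immune status 6 months after the last. Study Duration adds: "Research participants will be followed for safety for 12 months after the third study infusion".

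**The concern.** The human safety experience described was gathered at a much lower dose, and in Group 1 three of the four injections were intrathecal. The cells here come from unrelated donors. HLA type is determined but is not among the sample criteria, so a reaction that appears days or weeks later is a reasonable worry. The test at the start of injection is aimed at immediate reactions and would not reveal a delayed one.

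The plan collects information that could show a delayed reaction but attaches no decision to it. The monthly visits are described as evaluations of effect. Blood and urine tests are listed for inclusion, with no repeat scheduled after infusion in the available text. Safety follow-up has no stated review point. Under Expected Results, the absence of adverse reactions is assumed. Followed literally, the plan gives a child the second infusion on schedule, and starts new children, whatever has been seen after the first.

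**Working it through.** **1. Dose ratio.** Inputs: 20 to 50 million/kg (Stage 2, item 4); three infusions (Stage 3); 2 million/kg and four injections (background, Group 1).

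| Reading | Arithmetic | Ratio |
|---|---|---|
| Planned range per infusion, against 2 per injection | 20/2; 50/2 | 10 to 25 |
| Planned range for the course, against 2 per injection | (20/3)/2; (50/3)/2 | 3.3 to 8.3 |
| Planned range for the course, against a prior course of 4 × 2 = 8 | 20/8; 50/8 | 2.5 to 6.25 |
| Whole course both sides, planned range per infusion (3 × 20 = 60; 3 × 50 = 150) | 60/8; 150/8 | 7.5 to 18.75 |

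Rows 2 and 3 give the 2.5 to 8.3 quoted for a course-total reading. They take the prior 2 million/kg as the amount at each injection. If both figures are course totals, the ratio is again 10 to 25. The planned dose is higher under every reading. Rows 3 and 4 add intrathecal to intravenous doses, so they are comparisons of cell numbers, not safety margins.

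**2. Who is exposed before the first 1-month visit.** The plan's accrual figure reproduces: 10/3 = 3.3 weeks and 10/2 = 5.0 weeks, and at 2.5 per week 10/2.5 = 4.0, matching the stated 4 weeks or so. One month is 30/7 = 4.29 weeks. Further enrolments in that time are 2 × 4.29 = 8.6 to 3 × 4.29 = 12.9. Assume infusion promptly follows enrolment, and count the first child at day 0. If the rate refers to treated children only, 9 to 10 of the 10 have had a first infusion before the first child's 1-month visit. If it covers both groups, alternating, 9 to 13 children are enrolled and 4 to 7 of them treated. The plan gives the rate as an upper estimate, so accrual may be slower.

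**3. Where a check would act.** Infusions fall at about months 0, 1 and 2. Counted from the first infusion, the month 1 and month 2 assessments coincide with infusions 2 and 3. Counted from the end of treatment, no effect assessment falls between infusions, and only the cytokine tests do. Immune status comes at about 2 + 6 = 8 months, after all dosing. Of 10 × 3 = 30 planned infusions, 10 × 2 = 20 are second or third infusions.

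**4. What a pause after three children could show.** With no event in 3 children, the one-sided 95% upper limit on risk is 1 − 0.05^(1/3) = 0.63. At assumed risks per child of 10%, 20% and 30% (the documents give none), the chance of at least one event in three is 1 − (1 − p)³ = 0.27, 0.49 and 0.66. Multiplying by the 7p events expected in the other seven children gives 0.19, 0.68 and 1.38 first-infusion events averted. These are upper bounds: they assume one risk for all children, every event visible by 1 month, and that staff would otherwise carry on regardless.

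**The case against.** The strongest reply is that the plan is not without safeguards. Blood-group matching, infection and contamination screening, specialist review of contraindications and a test at the start of each injection all reduce risk. Inflammatory cytokines are measured at about the time infusions 2 and 3 are due. Clinicians would probably stop after a serious reaction without being told to. All of this narrows the gap. It does not close it, because no result is tied to a decision.

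A second reply is that item 4 is a criterion for choosing a sample, so the 10 to 25 ratio depends on an inference. That stands, and the lower range must be given beside it.

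Three stronger readings are tempting, and the documents do not support them:

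- **That the dose is unsafe.** The ratio shows only that the human experience described does not reach this exposure. The sponsor may hold data not described here, and part of the document was not available.
- **That safety is not monitored.** Twelve months of follow-up after the third infusion is planned. What is missing is a review that can change dosing.
- **That a three-child staggered start is required.** A clear result in three children excludes only risks above 63%. If those children received the low end of the range and risk rises with dose, it would say still less about the rest. The hold is a defensible choice, not a necessity.

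**Conclusion.** The point holds in limited form. The planned dose is 10 to 25 times the only human dose described if the range is per infusion, and about 2.5 to 8.3 times if it covers the course. No basis for the increase appears in the available text. No safety finding is a condition for the next infusion or the next child, and there is no stopping rule. The ratios rest on taking the cited 2 million/kg at face value, and the course-total range on its being given at each injection. The exposure counts rest on prompt infusion after enrolment. The gap in the rules depends on neither. This is an inexpensive improvement to patient safety, not a flaw that undermines the trial's analysis.

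**What to change.** 1. In Stage 2, item 4, write *per infusion* if that is what is meant; otherwise state the course total. If human intravenous data at this dose exist, cite them.
2. Before each second and third infusion, carry out an adverse-event check and review whatever results are available for that month. Withhold the infusion if there is a related serious adverse event or a sign of graft-versus-host reaction. Tie the check to the infusion day, since the visit times are counted from different starting points.
3. State that any such event pauses infusions in all children until it is reviewed. A body exists that could do this: the exclusion criteria already let one contraindication be set aside "according to the decision of the Medical Committee of the Center".
4. Record cells/kg and donor unit at each infusion, and list them for each child beside adverse events.

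**Cost.** About 20 short checks over the trial, with no extra children. Some infusions may be delayed, so the 1-month interval needs a stated window.

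**Optional.** Hold further first infusions after the first few children until their 1-month review. For three children this adds about 4.3 weeks to treated-group accrual, plus review time. If their second infusions also wait for that review, they may need a separate visit, and their infusions shift relative to the 2- and 3-month assessments. That matters in a comparison of 10 with 10 and should be reported. The protocol should also say that a clear review of three children does not establish that the dose is safe.
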